5.3 Exploratory Endpoints

- 1) Change in [REDACTED] assessed by [REDACTED] [REDACTED] at all post-baseline scheduled visits.
- 2) Proportion of CSU subjects with [REDACTED] each week.
- 3) Proportion of CSU subjects with [REDACTED] from Baseline in [REDACTED] at each week.
- 4) Proportion of CSU subjects with [REDACTED] from Baseline in [REDACTED] at each week.
- 5) Change from baseline in [REDACTED] as assessed by [REDACTED] at each week in CholU patients.
- 6) Change in weekly [REDACTED] over time.
- 7) Change in [REDACTED] at all post-baseline scheduled visits.

For weekly assessment, missing Week 10 and Week 22 scores will be imputed with LOCF.

5.4 PD Endpoint

- 1) Peripheral blood eosinophils.

5.5 Pharmacokinetic Endpoint

- 1) Blood samples will be analyzed for AK002 plasma concentrations and ADA.

5.6 Safety Endpoints

- 1) Safety endpoints include physical examination
- 2) routine safety laboratory assessments
- 3) vital signs
- 4) electrocardiogram (ECG)
- 5) urine safety, and
- 6) adverse event reporting (Visits 2–7).

6. Statistical Methods

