Centers/Countries	Approximately 4 study centers in the USA and Germany. Only the sites in Germany will participate in the extension study.
Number of Subjects	
N (total) = Approximately 48 subjects with chronic urticaria
 
This will include the following cohorts:
 
 
• Approximately 12 subjects with Cholinergic urticaria (CholU)
 
• Approximately 12 subjects with Urticaria factitia (UF)
 
• Approximately 12 XOLAIR® (omalizumab) naïve subjects with Chronic spontaneous urticaria (CSU)
 
• Approximately 12 subjects with Chronic spontaneous urticaria (CSU) who did not achieve an adequate response on XOLAIR® (omalizumab) in the opinion of the Investigator
 
 
The extended dosing will be applicable only to the subjects in the CholU, UF, and CSU-XOLAIR® (omalizumab) failure cohorts.

Rationale for Sample Size	The planned sample size of approximately 48 subjects is based on common practice in early phase, proof-of-concept studies.
Duration of Patient Participation and Duration of Study	
The total study duration for each patient will be approximately 32 weeks. This includes:
 
 
• A screening period of 4 weeks prior to study drug administration
 
• Administration of study drug at Day 1, Day 29, Day 57, Day 85, Day 113, and Day 141
 
• Follow-up through Day 197 (8 weeks post last dose)
 

Duration of Patient Participation and Study cont.	Subjects who elect to receive optional extended dosing with up to 12 additional doses of AK002 will participate for up to an additional 12 months (see Appendix 2 ).

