Concomitant Medications	Second-generation H1-antihistamines as concomitant medication once daily and up to 4 times daily on demand (drug intake to be documented in the patient diary).
Safety Evaluations	
Safety and tolerability will be assessed throughout the study by monitoring and evaluating adverse events (AEs), including any complications resulting from the IV infusion. All treatment-emergent adverse events (TEAEs) will be collected from the start of study drug administration through 8 weeks after last dose received or Early Termination (ET). Severity will be assessed using the National Cancer Institute (NCI) Common Terminology Criteria for Adverse Events (CTCAE) Version 4.03. All AEs will be assigned a severity grade and relationship to study drug.
 
Additional safety evaluations include clinical laboratory tests, including anti-drug antibody to AK002, complete blood counts, chemistries, and urinalyses, ECGs; and vital signs.

Statistical Methodology	All subjects who received a dose of study drug will be included in the analysis. All safety data will be listed. Where appropriate, summary statistics will be provided (number of non-missing values, mean, median, standard deviation, minimum, and maximum for continuous variables, and number and percentage for categorical variables) for all measures, including demographic and baseline values, clinical scores and safety endpoints.
Rationale for Amendment 4.1	
The following modifications have been incorporated into Amendment 4.1 of the protocol.
 
 
• Procedures that allow subjects in the CholU, UF, and CSU-XOLAIR® (omalizumab) failure cohorts who received all 6 infusions of AK002, were followed through Day 155, and demonstrated severe symptoms of urticaria following discontinuation of treatment, to be offered the option to receive extended dosing with up to 12 additional doses of AK002. Offering extended dosing allows subjects with no other treatment options continued access to AK002 and the benefit obtained during the initial 6 infusions. It also allows for collection of longer-term efficacy, safety, and tolerability data of AK002.
 
• PK will be analyzed retroactively using backup blood samples.
 

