### 5.2 Other Endpoints

- 1) Safety of subjects treated with AK002: This includes physical examination, routine safety laboratory assessments, vital signs, electrocardiogram (ECG), urine safety, and adverse event reporting (Visits 2–10)
- 2) Change in disease activity as assessed by UAS7 and/or [REDACTED] (from Baseline to Visits 3, 5, 8, and 10)
- 3) Change in number of symptom-free days per week (patient diary-based CSU score; wheals, flares, itch, avoidance behavior) from Baseline to Visits 3, 5, 8, and 10
- 4) Change in [REDACTED] assessed by [REDACTED] from Baseline to Visits 3, 5, 8, and 10
- 5) Change in number of intake of rescue medication from Baseline to Visits 3, 5, 8, and 10
- 6) In case of [REDACTED], change in [REDACTED] from Visit 2 to Visit 3, 5, 8, and 10, as assessed by [REDACTED]
- 7) Change in number of [REDACTED] from Baseline to Visits 3, 5, 8, and 10
- 8) Change in [REDACTED] from Baseline to Visits 3, 5, 8, and 10
- 9) Changes in trigger threshold from Baseline to Visits 2, 3, 5, 8, and 10, as assessed by Pulse Controlled Ergometry Test (PCE) and FricTest®, as applicable
- 10) Rates of complete response, partial response, and non-response based on UCT, [REDACTED], trigger thresholds (where applicable), and QoL from Baseline to Visits 3, 5, 8, and 10
- 11) Serum levels at baseline and change from Baseline to Visits 3, 5, 8, and 10 of serum levels of potential biomarkers in AK002-treated subjects (e.g., tryptase, eosinophils, total IgE, basophils, eosinophil cationic protein)
- 12) Rates of AK002-treated subjects with relapse, rebound, sustained treatment effects at Visit 7

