### **6.1.2 Treatment Period**

During the Treatment Period, all eligible subjects will receive AK002 by IV infusion every 28 days. The first dose will be administered at the beginning of the treatment period Day 1 (Visit 2) after baseline measurements. At Day 141 ( $\pm 2$  days) (Visit 7), the final dose of AK002 will be given. Throughout the treatment period, subjects must maintain stable doses of their baseline AH dose and treatment regimen and remain on a stable treatment regimen through the end of the study. Patient's use of rescue medication will be monitored and reviewed throughout the treatment period and if necessary adjusted according to the current urticaria guidelines ([Zuberbier, 2014](#)). Subjects are expected to attend all site visits based on the assessment schedule (see [Table 3](#)).

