3.1 General Description

This is an open-label, pilot study to assess the efficacy and safety of AK002 in subjects with antihistamine-resistant chronic urticaria. The study comprises a screening period of 4 weeks, with daily oral intake of standard-dose (once daily) second-generation antihistamine (AH) (standard of care, with on-demand intake of up to 3 additional AH tablets per day). The treatment period comprises a daily oral intake of standard-dose second-generation AH and AK002 administered by IV infusion at Days 1, 29, 57, 85, 113, and 141. The primary and secondary endpoints will be evaluated at Week 10, 2 weeks after last dose, for subjects enrolled under Protocol Amendment 2.1 and Week 22, 2 weeks after last dose, for all remaining subjects (i.e., those on study during Protocol Amendment 3), and then patients will be followed for an additional 4 weeks (Week 24). The study design is presented schematically in [Table 1](#).

Table 1 Schedule of Assessments for the Main Study

Description	Visit 1	Visit 2	Visit 3	Visit 4	Visits 5, 6, 7	Visit 8	Visit 9	Visit 10
	Day -28	Day 1	Day 29 (± 2)	Day 57 (± 2)	Days 85, 113, and 141 (± 2)	Day 155 (± 2)	Day 169 (± 2)	Day 197 (± 2)
	Week -4	Week 0	Week 4	Week 8	Weeks 12, 16, and 20	Week 22	Week 24	Week 28
	Screening	Baseline/Dosing	Dosing	Dosing	Dosing ^r	Response Assessment ^t	Response Assessment	End of Study/ Early Term.
Informed consent	x ^a							
Eligibility assessment/ confirmation	x	x ^b						
Demographic data	x							
Medical history	x							
Prior CU treatment	x							
Prior/concomitant medication	x	x	x	x	x	x	x	x
Rescue medication use		x	x	x	x	x	x	x
Study Drug administration ^c		x	x	x	x			
Patient diary ^{d,s}	x	x	x	x	x	x	x	x
UAS7		x	x	x	x	x	x	x
		x	x	x	x	x	x	x
		x	x	x	x	x	x	x
UCT		x	x	x	x	x	x	x
q	x	x	x	x	x	x	x	x
		x	x	x	x	x	x	x
		x	x	x	x	x	x	x
		x	x	x	x	x	x	x
and FricTest® ^e	x (if applicable)	x (if applicable)	x (if applicable)	x (if applicable)				
Skin biopsy ^p		x				x		

Table 1 Scheduled of Assessments (continued)

Description	Visit 1	Visit 2	Visit 3	Visit 4	Visits 5, 6, 7	Visit 8	Visit 9	Visit 10
	Day -28	Day 1	Day 29 (± 2)	Day 57 (± 2)	Days 85, 113, and 141 (± 2)	Day 155 (± 2)	Day 169 (± 2)	Day 197 (± 2)
	Week -4	Week 0	Week 4	Week 8	Weeks 12, 16, and 20	Week 22	Week 24	Week 28
	Screening	Baseline/Dosing	Dosing	Dosing	Dosing ^r	Response Assessment ^t	Response Assessment	End of Study/ Early Term.
Anti-drug antibodies ^f		x	x		x	x		x
PK analysis ^f		x	x		x	x		x
Blood safety ^g	x	x	x	x	x	x	x	x

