3.9 Safety Assessments

3.9.1 Physical Examination

Physical examinations will be conducted at Visits 1 to 7. Clinically significant findings will be reported as adverse events.

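### SAP 5.6 ends the adverse-event endpoint at Visit 7, which on the six-dose schedule is the day of the last infusion; the protocol and the SAP's own Table 1 run to Visit 10, and SAP 6.6 uses the same Visit 7 limit to start the final analysis

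*SAP*

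**What the plan says.** **Stated endpoint.** SAP 5.6 gives item 6 of the safety endpoints as "adverse event reporting (Visits 2–7". Protocol 5.2 ends the corresponding item with "urine safety, and adverse event reporting (Visits 2–10", and the synopsis has the same range.

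**What Visit 7 is.** Protocol 6.1.2 places the last infusion at Day 141 ("Visit 7), the final dose of AK002 will be given"). Protocol Table 1 and SAP Table 1 put Visits 8, 9 and 10 at Days 155, 169 and 197.

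**How long events are collected.** The synopsis says that treatment-emergent events "will be collected from the start of study drug administration through 8 weeks after last dose received or Early Termination (ET", and it describes the participation period as "Follow-up through Day 197 (8 weeks post last dose". Protocol 11.6.1 records all events to Day 197 or Early Termination. SAP Table 1 marks adverse events at every visit from 2 to 10.

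**Other places with a short window.**
- SAP 3.9.1: "Physical examinations will be conducted at Visits 1 to 7".
- SAP 3.9.6: urine pregnancy tests at Visits 2 to 7.
- SAP 6.6: summary and analysis begin when all subjects have completed Visit 7, or discontinued before it, and the database is cleaned and locked.
- SAP 3.1, after the Week 22 evaluation: "and then patients will be followed for an additional 4 weeks (Week 24".

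**Precedence.** Protocol 13 lets the SAP prevail where the analyses differ. SAP 1 says that it supersedes the protocol's statistical methods. SAP 3.7 declares no changes to the planned analyses.

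**The concern.** The document that governs the analysis states an adverse-event window that closes on the day of the last infusion, and SAP 3.7 neither declares nor justifies a change from the protocol. Taken literally, a reaction that begins after the sixth infusion visit is outside the endpoint, although the protocol schedules three further visits to look for it. A programmer has to choose between the window in 5.6 and the one in Table 1.

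The same visit number controls the timing of the final analysis. If 6.6 is applied to the current schedule, the visit condition is met before the Week 22 assessment, where the primary endpoint is measured, and before any post-treatment safety follow-up.

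**Working it through.** **Inputs.** Visit days from SAP Table 1 and Protocol Table 1: Visit 2 = Day 1, Visit 7 = Day 141 (Week 20), Visit 8 = Day 155 (Week 22), Visit 9 = Day 169 (Week 24), Visit 10 = Day 197 (Week 28). Visits 7 and 10 each have a window of ±2 days.

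**1. Reproduce the plan's own figure.** The synopsis gives 8 weeks from last dose to end of follow-up. 197 − 141 = 56 days, and 56 / 7 = 8.0 weeks, an exact match.

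**2. Size of the gap.**
- Visits 2 to 7 span 141 − 1 = 140 days.
- Visits 2 to 10 span 197 − 1 = 196 days.
- Outside the stated window: 196 − 140 = 56 days, and 56 / 196 = 28.6%.
- With both visit windows at their extremes: 56 − 4 = 52 to 56 + 4 = 60 days.
- Scheduled visits outside the window: 8, 9 and 10, three of the nine from Visit 2 onward.

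**3. The analysis trigger in SAP 6.6.** From Visit 7 to the Week 22 assessment is 155 − 141 = 14 days; from Visit 7 to the end of follow-up is 56 days. The visit condition can therefore be met that far ahead of both.

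**4. The follow-up text in SAP 3.1.** Week 22 + 4 weeks = Week 26, not Week 24. SAP 3.2.2 gives 8 weeks of follow-up after treatment: Week 20 + 8 = Week 28, which agrees with Table 1. The sentence in 3.1 agrees neither with itself nor with those two places.

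**5. Where the Visit 7 limit may come from (an inference).** SAP 7.7.1 lists UCT visits at Weeks 4, 8, 10, 12 and 16 for Amendment 2.1 subjects, and SAP 3.1 describes Week 10 as 2 weeks after their last dose. The last dose was then at Week 10 − 2 = Week 8. If Visits 1 and 2 were screening and baseline, as now, and UCT was recorded at every later visit, the five weeks are Visits 3 to 7. Visit 7 is then Week 16, and 16 − 8 = 8 weeks after the last dose. On that numbering, Visits 2 to 7 cover the whole follow-up for Amendment 2.1 subjects but stop at the last infusion for six-dose subjects.

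**6. What the operative analysis rules do with an event on, say, Day 160.**
- Collected: yes (Protocol 11.6.1; SAP Table 1).
- Treatment-emergent: yes. SAP Table 4 sets a start and no end.
- Tabulated and listed: yes. SAP 7.10.1 summarizes treatment-emergent events and lists all events with no visit limit.

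**The case against.** The strongest reply is that this is an editorial slip with no shown effect on any output, because step 6 has the Day 160 event collected, counted and listed. That reply stands as far as it goes. A reader might infer from 5.6 that events after Day 141 will be dropped from the tables; the SAP's working rules do not support that. A missing end date in the treatment-emergent definition includes late events rather than excluding them.

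A reader might also infer that all safety data after the last infusion fall outside the endpoint. They do not. The bracket in 5.6 belongs to the adverse-event item alone. SAP 3.9.2, 3.9.3 and 3.9.5 take vital signs, laboratory tests and ECGs at all visits, and 7.10.2 to 7.10.4 summarize them by visit.

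Two further objections are sound. SAP precedence covers analyses, so 3.9.1 and 3.9.6, which describe conduct, cannot shorten what the protocol schedules. And writing Visits 2 to 10 for everyone could be wrong for Amendment 2.1 subjects, for whom Visits 2 to 7 may be correct.

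The objection does not remove the contradiction between 5.6 and Table 1, and it does not answer 6.6. The requirement for a cleaned and locked database softens that trigger, but nothing in 6.6 says that lock waits for Visit 10.

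**Conclusion.** The point holds as a wrong stated window and an internal contradiction in the SAP. For subjects on the six-dose schedule, 56 of 196 days (28.6%; 52 to 60 days with visit windows) and Visits 8 to 10 are outside the adverse-event endpoint as written. Loss of events is not demonstrated.

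It should be corrected because the limit recurs and, above all, because in 6.6 it allows the visit condition for the final analysis to be met before the Week 22 assessment and all follow-up.

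The day counts rest only on the scheduled visit days. That the limit is a leftover from Amendment 2.1 is an inference from the visit weeks in SAP 7.7.1 and the dosing remark in SAP 3.1, and assumes that visits were numbered then as they are now.

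**What to change.** In the SAP:
- **5.6:** state Visits 2 to 10, ending at Day 197 or the Early Termination visit, for subjects on the six-dose schedule. Give the Amendment 2.1 range separately, after confirming that schedule's visit numbers.
- **6.6:** make the trigger completion of the final follow-up visit (Visit 10, or the final visit under Amendment 2.1), or earlier discontinuation. Keep the database-lock condition.
- **3.9.1 and 3.9.6:** reconcile the visit ranges with Table 1.
- **3.1:** reconcile the Week 24 follow-up text with Week 28 in Table 1 and the 8 weeks in 3.2.2.
- **Table 4 (optional):** an end bound on the treatment-emergent definition is not needed to capture late events. If one is added, set it at the end-of-study or Early Termination visit rather than at a fixed 8 weeks. Visit 10 may fall as late as Day 199 (197 + 2), and for a Day 141 last dose a cut at Day 197 could exclude an event with onset on Day 198 or 199.

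The cost is SAP wording. The visits are already scheduled and the events already recorded, so data collection does not change. If lock had been planned around Visit 7, the final analysis would move by up to 8 weeks.

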6.1 General Methodology

All statistical analyses will be conducted using SAS Version 9.4 or later on the Microsoft® Windows Operating System.

Continuous data will be summarized using n (number of subjects with non-missing observations), mean, median, standard deviation (SD), minimum value, and maximum value. Categorical data will be summarized using the frequency count and percentage (n, %) of subjects in each category. Number of subjects with non-missing values and number of subjects with missing values (e.g., Not Done) will be presented, where appropriate. Subjects with missing values will not contribute to the denominator of percentage calculations. Counts of zero in any category will be presented without percentage.

All endpoints will be summarized by the individual applicable cohorts (CholU, UF, CSU-XN or CSU-XF). Where appropriate, the summaries will also be carried out for all 4 cohorts combined.

Two-sided 95% confidence interval (CI) may be presented for the mean or percentage.

The precision rules for the presentation of summary statistics will be:

- Sample size (n, N) and number of missing responses (if displayed) – Integer
- Mean, CI – One more decimal place than reported/collected
- Standard deviation – Two more decimal places than reported/collected
- Median, other percentile, minimum, maximum – Same number of decimal places as reported/collected
- Ratio – two decimal places
- Percentage – one decimal place generally, or two decimal places for <0.1%

The data summaries will be accompanied by individual subject data listings. All data available from diary, questionnaires, eCRF, and external transfer (e.g., labs) will be listed and will include relevant and pertinent subject information, e.g. study day. The listings will be sorted in the order of Cohort and unique subject ID, and assessment name and assessment date/time.

Dates will be presented in the ISO-8601 format YYYY-MM-DD. Times will be displayed in 24-hour clock format. Numbering for tables, figures and listings will follow ICH E3 Guidelines ([ICH, 1996](#)).

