5.1 Primary Endpoint

- 1) The primary efficacy endpoint is the change in Urticaria Control Test (UCT) for each population (CSU-XN, CSU-XF, UF, and CholU). The UCT is a score for symptom control in chronic urticaria, from Day 1 (baseline) to Week 10 for subjects enrolled under Protocol Amendment 2.1 and Week 22 for all remaining subjects (i.e., those on study during Protocol Amendment 3). A change of the UCT score of 3 or more points is regarded as clinically relevant (minimal clinically important difference [MCID]). If Week 10 or Week 22 measures

are not available, they will be imputed with last observation carried forward method (LOCF). The data summary will include Week 10 and Week 22 derived from the available data and Week 10/LOCF and Week 22/LOCF derived from the available plus the imputed data.

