5.2 Secondary Endpoints

- 1) Proportion of subjects with CR, CMR, and DC based on UCT (all patients) at all time points. Section 4 provides the definition of CR, CMR, and DC.
- 2) Change from baseline in disease activity as assessed by UAS7 at each week in CSU patients. If Week 10 or Week 22 measures are not available, they will be imputed with the last non-missing weekly UAS7 (LOCF). The data summary will include Week 10 and Week 22 derived from the available data and Week 10/LOCF and Week 22/LOCF from the available plus the imputed data.

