7.7 Efficacy Analyses

7.7.1 Primary Efficacy Analysis

The primary efficacy variable is the change from baseline in UCT score for each population (CSU-XN, CSU-XF, UF, and CholU). UCT score and its change from baseline will be summarized using descriptive statistics by study visit (Weeks 4, 8, 10, 12, 16 for subjects enrolled under Protocol Amendment 2.1 and Weeks 4, 8, 12, 16, 20, 22, 24, and 28 for subjects enrolled after Protocol

Amendment 3). A 95% CI for the mean change will be computed. The summaries will be provided for each cohort.

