7.7.1.3 Secondary Efficacy Analyses

All summaries will be provided for each cohort.

- 1) Subjects achieving UCT CR and CMR will be tabulated with % of subjects for each visit. Subjects achieving a maximum of 0, 1, 2, 3, or 4 responses over the 8 post-baseline visits (subjects enrolled under Protocol Amendment 3) will also be tabulated. A 95% CI for the % responses will be calculated using the binomial distribution. Subjects achieving UCT DC will be similarly summarized.
- 2) Changes from baseline in UAS7 in CSU patients will be summarized similarly for each week the diary is collected. A 95% CI for the mean change will be reported. This analysis will also be carried out in the subgroup of CSU-XN patients with baseline UAS7 ≥ 16 .

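### UCT response rates (CR, CMR, DC) are planned on observed cases only, so they are biased whenever loss differs by response status; report a full-denominator rate beside them

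*SAP*

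**What the plan says.** The general rule is in SAP section 6.1: "Subjects with missing values will not contribute to the denominator of percentage calculations". The same section shows missing counts where appropriate and lists all questionnaire data by subject.

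The rates concerned are the first secondary endpoint in SAP section 5.2: "Proportion of subjects with CR, CMR, and DC based on UCT (all patients) at all time points". SAP section 7.7.1.3 says "Subjects achieving UCT CR and CMR will be tabulated with % of subjects for each visit", treats disease control in the same way and adds a binomial 95% confidence interval. Neither place names a denominator, an analysis set or an imputation.

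LOCF is written for three other quantities:
- the primary endpoint, change in UCT, where missing Week 10 or Week 22 measures "are not available, they will be imputed with last observation carried forward method (LOCF" (SAP section 5.1);
- UAS7, where "they will be imputed with the last non-missing weekly UAS7 (LOCF" applies (SAP section 5.2, item 2);
- the exploratory weekly scores: "For weekly assessment, missing Week 10 and Week 22 scores will be imputed with LOCF" (SAP section 5.3).

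SAP section 6.4, although titled for dropouts, deals with scaling of item and daily scores, partial dates and missing adverse event attributes. It does not cover a missed visit for a responder endpoint. SAP section 4 defines all three response categories from the UCT score.

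**The concern.** Dropping subjects without a score estimates the response rate among those who stayed. That equals the rate in everyone treated only if staying is unrelated to response. Protocol section 9.4 lists lack of efficacy among the reasons for withdrawal, so outcome-related loss is foreseeable. There is no control arm to offset it, and each cohort has about 12 subjects, so one or two losses move a rate visibly. The planned binomial interval does not reflect this error.

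Three further gaps affect who is counted.

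- **Early termination.** Leavers receive the final-visit assessments (protocol section 10), and the Visit 10 column of protocol Table 3 serves both end of study and early termination. SAP section 6.2 has no visit windows and analyses data under the visit to which they belong. No passage says whether a leaver's UCT is then a Week 28 value.
- **Amendment groups.** SAP section 5.1 assigns "Week 22 for all remaining subjects (i.e., those on study during Protocol Amendment 3", while section 7.7.1 gives "Weeks 4, 8, 12, 16, 20, 22, 24, and 28 for subjects enrolled after Protocol" Amendment 3. A subject enrolled under Amendment 2.1 and still on study during Amendment 3 could fall under either schedule, so the denominator at Weeks 10 and 22 is not fixed.
- **Item threshold.** SAP section 3.8.1 makes the UCT total missing at one blank item, protocol section 10.4.2 only at more than one. SAP section 3.7 declares no changes.

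**Working it through.** The plan states no response or dropout rate, so it has no figure of its own to reproduce beyond 4 cohorts × 12 = 48 subjects (SAP section 3.3). The cohort size of 12 comes from the SAP. All response and loss counts below are assumptions.

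**Counts.** Take 12 subjects and 6 true responders: 6/12 = 50%, exact (Clopper-Pearson) 95% CI 21% to 79%. The observed-case rate is responders seen / subjects seen. The full-denominator rate is responders seen / 12.

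| Lost | Observed cases | Full denominator, missing = non-response |
|---|---|---|
| 1 non-responder | 6/11 = 55% | 6/12 = 50% |
| 2 non-responders | 6/10 = 60% | 6/12 = 50% |
| 3 non-responders | 6/9 = 67% | 6/12 = 50% |
| 1 responder | 5/11 = 45% | 5/12 = 42% |
| 2 responders | 4/10 = 40% | 4/12 = 33% |
| 2 of each | 4/8 = 50% | 4/12 = 33% |

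If LOCF is applied at Week 22, losing three non-responders gives 6/12 = 50% and losing one responder also gives 6/12 = 50%, provided that each last score matches the subject's true status.

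**Expected bias.** Let p be the true rate, q1 the chance that a responder's score is missing and q0 the same for a non-responder.

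- Observed cases: p(1 − q1) / [p(1 − q1) + (1 − p)(1 − q0)] − p
- Missing counted as non-response: p(1 − q1) − p = −p·q1

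With p = 50%:

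| q0 | q1 | Observed-case bias (points) | Non-response bias (points) |
|---|---|---|---|
| 20% | 0% | +5.6 | 0.0 |
| 20% | 5% | +4.3 | −2.5 |
| 30% | 5% | +7.6 | −2.5 |
| 20% | 10% | +2.9 | −5.0 |
| 20% | 20% | 0.0 | −10.0 |
| 5% | 20% | −4.3 | −10.0 |

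For the fourth row: 0.45 / (0.45 + 0.40) = 52.9%, so +2.9; and 0.45 − 0.50 = −5.0. Observed-case bias is zero when q0 = q1 and otherwise takes the sign of q0 − q1. Non-response counting is never too high. It is closer to the truth when responders are rarely lost, and further from it when they are lost too.

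**Early-termination timing.** Protocol section 9.1 sets the visit 28 days after the last dose, or earlier if necessary, or as soon as possible if 28 days have already passed. As one example, a last dose on Day 57 puts it at Day 57 + 28 = Day 85. The scheduled Week 28 visit is Day 197, which is 197 − 85 = 112 days = 16 weeks later. If one such score met the response definition and were filed as Visit 10, a Week 28 rate of 5/12 = 42% under the full denominator would read 6/12 = 50%.

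**The case against.** The strongest objection is that the remedy can be worse than the rule. This stands: under equal loss, observed cases are unbiased and non-response counting is not, and the documents give no dropout pattern from which to choose. It is why the non-response rate should be labelled conservative and never shown alone.

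Second, LOCF may already cover Weeks 10 and 22. SAP section 5.1 imputes the UCT score there, and the response categories are functions of that score. Repeating LOCF for UAS7 was needed because UAS7 is a different variable, so silence on the UCT rates does not prove exclusion. That is a fair reading of two visits, but the SAP does not state it and it reaches no other visit.

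Third, the harm is limited. There are no hypothesis tests, the rates are secondary, treatment discontinuers are asked to return for final assessments, and with about 12 subjects per cohort a reader can largely rebuild the full-denominator rate from the listings. This also stands, and it limits the weight of the point. It does not supply a rule.

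A reader might infer that every leaver's last score will be reported as Week 28, or that it is always taken 28 days after the last dose. Neither is supported: filing is left open, protocol section 9.3 sends treatment discontinuers to post-treatment follow-up procedures, and the timing varies. A reader might also take the two UCT item thresholds as unresolved. They are not: protocol section 13 and SAP section 1 both give the SAP precedence. What remains is an undeclared change that enlarges the missing set.

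**Conclusion.** The point holds as a gap in a stated rule. Observed-case denominators govern the UCT response rates by default, and those rates are biased when, and only when, loss differs by response status. Under the assumed patterns at a true rate of 50%, the expected bias runs from −4.3 to +7.6 points. In a single cohort of 12, one to three one-sided losses of non-responders move 50% to between 55% and 67%. All these shifts lie inside the exact interval for 6/12, and all rest on assumed losses.

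Two stronger readings should be resisted. One is that the rule inflates the rates: the direction depends on who leaves, and the documents do not say. The other is that the primary result is affected: it is a mean change, shown both observed and with LOCF, and a denominator rule for percentages does not touch it.

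The change is worth making because it is cheap and puts the uncertainty on the page. It does not rescue an invalid analysis.

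**What to change.** **SAP sections 6.1 and 7.7.1.3.** For UCT complete response, clinically meaningful response and disease control at each visit, report three things together:
- a conservative rate whose denominator is every dosed subject scheduled for that visit, with a missing UCT counted as non-response; state that this set is wider than MITT, which requires a post-baseline UCT, and that it agrees with the protocol synopsis, which includes everyone dosed;
- the observed-case rate, always with the number missing;
- at Weeks 10 and 22, the rate based on the LOCF score.

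State the limitation next to the conservative rate. It is lowered by the share of all subjects who are responders with a missing score, so it can be further from the truth than the observed-case rate when responders are lost as well.

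**SAP section 6.2.** State that an early-termination UCT does not count as Week 28 unless it was taken at the scheduled Week 28 visit.

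**Minor.** Use one wording for the amendment groups in SAP sections 5.1, 7.7.1 and 7.7.1.3, so that each subject has one schedule and each visit a defined denominator. Declare in SAP section 3.7 that the UCT item threshold differs from protocol section 10.4.2. This matters more once missing counts as failure, because a single blank item would then make a non-responder.

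**Cost.** SAP text and additional table rows; no new data. The price is that a dropout unrelated to efficacy, or one missed visit, counts against the drug in the conservative rate, which is why the other two rates stay beside it.
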